9.3 Populations for Analyses

For purposes of analysis, the following populations are defined in [Table 15](#).

Table 15 Populations for Analyses

Population	Description
Safety Evaluable Population	For Parts 1 and 2, all patients who receive any amount of study drug (NL-201) will be considered evaluable for safety regardless of the duration of NL-201 treatment. This population is defined for Part 1, and Part 2. For Parts 3 and 4, all patients who receive any amount of study drug (NL-201 or pembrolizumab) will be considered evaluable for safety regardless of the duration of treatment. This population is defined for Part 1 and Part 3, and Part 2 and Part 4, expansion cohorts. This population will be used to summarize safety parameters.
Efficacy Evaluable Population	For Parts 1 and 2, all patients with measurable disease by RECIST, who receive any amount of study drug (NL-201) or who discontinue study drug early due to disease progression and/or death will be considered evaluable for efficacy. For Parts 3 and 4, all patients with measurable disease by RECIST, who receive any amount of study drug (NL-201 or pembrolizumab) or who discontinue study drug early due to disease progression and/or death will be considered evaluable for efficacy. This population is defined for Part 1 and Part 3, and Part 2 and Part 4.
DLT-Evaluable Population	Patients enrolled into Part 1 or Part 3 who either complete the first 21 days of study or who experience a DLT.

DLT = dose limiting toxicity; RECIST = Response Evaluation Criteria in Solid Tumors

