A mTPI design will be used to guide dose escalation and de-escalation within each schedule, with the final decision regarding dose assignment being made by the DMC. In Schedule A, patients will be dosed every 21 days, while in Schedule B patients will be dosed on Days 1 and 8 of every 21-day cycle.

Part 1 (NL-201 IV Monotherapy)

Assessment of toxicity and dose escalation or de-escalation as guided per the mTPI will be made after all DLT-evaluable patients have completed Cycle 1 and the DMC has reviewed the safety data. If dose escalation or dose de-escalation is indicated per mTPI, the DMC will recommend the next dose level. Dose escalation and de-escalation will occur independently for cohorts of each schedule. The proposed starting dose for NL-201 IV will be the lowest pharmacologically active dose (PAD) and is 150- to 300-fold below the C_{max} achieved in monkey.

Monotherapy Cohorts (21-day cycles)		NL-201 dose level ($\mu\text{g}/\text{kg}$)	Maximum dose that may be administered at 1 time (μg) ^a
Schedule A (D1)	Schedule B (D1+D8)		
Planned NL-201 Dose Levels^b			
1A	1B	0.1	10
2A	2B	0.3	30
3A	3B	1.0	100
4A	4B	3.0	300
5A	5B	6.0	600
6A	6B	12.0	1200
Potential NL-201 Intermediate Dose Levels^b			
2A-1	2B-1	0.6	60
3A-1	3B-1	1.5	150
3A-2	3B-2	2.0	200
4A-1	4B-1	4.0	400
4A-2	4B-2	5.0	500
5A-1	5B-1	7.5	750
5A-2	5B-2	9.0	900
5A-3	5B-3	10.0	1000

D = day; DMC = Data Monitoring Committee

Monotherapy Cohorts (21-day cycles)		NL-201 dose level (µg/kg)	Maximum dose that may be administered at 1 time (µg) ^a
Schedule A (D1)	Schedule B (D1+D8)		
a Applicable to patients that weigh ≥ 100 kg (dose is capped as to not allow > 100 times the current dose level to be administered to a patient at 1 time).			
b At the recommendation of the DMC or based on Sponsor's determination, additional intermediate dose levels may be tested and/or cohorts may be expanded.			

The maximum tolerated dose (MTD) is defined as the highest dose for which the probability of a patient experiencing a DLT with NL-201 during Cycle 1 is ≤ 33%. At the discretion of the DMC, and in keeping with the pre-specified mTPI design matrix, additional dose levels may be tested to determine the MTD.

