Based on review of DLTs, the DMC may initiate step-dosing to improve the tolerability of NL-201, wherein 1 or more step-doses below the target dose would be provided prior to reaching the target dose (see Section 6.2.1.4). If step-dosing is used, the DLT window would extend from the first dose to 21 days after receiving the target dose (ie, would include the initial reduced-dose cycles in addition to the first target-dose cycle). Once a patient receives the intended target dose for their cohort, subsequent doses for that patient will continue at that dose level unless a delay in dosing of > 6 weeks causes washout of the drug, in which case the step-dosing regimen would be repeated if the patient is to resume dosing.

The DMC will determine the RP2D and treatment schedule (either A or B) for Part 2 by considering the PK, PDn, safety and tolerability, antitumor activity, and the occurrence of any cumulative toxicities over multiple cycles of NL-201.

Part 3 (NL-201 in Combination with Pembrolizumab)

Schedule A: Dosing of pembrolizumab and NL-201 will occur on Day 1 of each 21-day cycle. A fixed dose of 200 mg pembrolizumab will be administered before NL-201. NL-201 infusion will start 30-60 minutes after pembrolizumab infusion is complete.

Schedule B: Dosing of pembrolizumab will occur on Day 1 of each 21-day cycle. Dosing of NL-201 will occur on Day 1 and Day 8 of each 21-day cycle. On Day 1, a fixed dose of 200 mg pembrolizumab will be administered before NL-201. NL-201 infusion will start 30-60 minutes after pembrolizumab infusion is complete.

Combination Cohorts (21-day cycles)				Maximum dose of NL-201 that may be administered at 1 time (µg) ^a
Schedule A (D1)	Schedule B (D1+D8)	Pembrolizumab (D1)	NL-201 dose level (µg/kg)	
Planned NL-201 Dose Level				
P-1A	P-1B	200 mg	0.3	30
P-2A	P-2B	200 mg	1	100
P-3A	P-3B	200 mg	3	300
P-4A	P-4B	200 mg	6	600
P-5A	P-5B	200 mg	12	1200

Potential NL-201 Intermediate Dose Level^b				
P-2A-1	P-2B-1	200 mg	0.6	60
P-3A-1	P-3B-1	200 mg	1.5	150
P-3A-2	P-3B-2	200 mg	2.0	200
P-4A-1	P-4B-1	200 mg	4.0	400
P-4A-2	P-4B-2	200 mg	5.0	500
P-5A-1	P-5B-1	200 mg	7.5	750
P-5A-2	P-5B-2	200 mg	9.0	900
P-5A-3	P-5B-3	200 mg	10.0	1000

D = day; DMC = Data Monitoring Committee

- a Applicable to patients that weigh ≥ 100 kg (dose is capped as to not allow > 100 times the current dose level to be administered to a patient at 1 time)

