6.2 Dose Modification

6.2.1 Dose-Cohort Study Escalation, De-Escalation, and Stopping Rules

6.2.1.1 Part 1: Dose Escalation Study of NL-201 Monotherapy

In Part 1, an mTPI²⁵ will be used to guide dose escalation and de-escalation within each schedule (ie, IV Schedule A, IV Schedule B), with the final decision regarding dose assignment being made by the DMC. In IV Schedule A, patients will be dosed every 21 days, while in IV Schedule B patients will be dosed on Days 1 and 8 of every 21-day cycle. The mTPI design matrix is shown in Figure 5.

Figure 5 mTPI Design Matrix for Part 1

Number of DLT	Number of enrollment at current dose level													
	2	3	4	5	6	7	8	9	10	11	12	13	14	15
0	E	E	E	E	E	E	E	E	E	E	E	E	E	E
1	S	S	S	S	E	E	E	E	E	E	E	E	E	E
2	DU	D	S	S	S	S	S	S	E	E	E	E	E	E
3		DU	DU	D	S	S	S	S	S	S	S	S	S	E
4			DU	DU	DU	D	S	S	S	S	S	S	S	S
5				DU	DU	DU	DU	D	S	S	S	S	S	S
6					DU	DU	DU	DU	DU	D	S	S	S	S
7						DU	DU	DU	DU	DU	DU	D	S	S
8							DU	DU	DU	DU	DU	DU	DU	DU
9								DU	DU	DU	DU	DU	DU	DU
10									DU	DU	DU	DU	DU	DU
11										DU	DU	DU	DU	DU
12											DU	DU	DU	DU
13												DU	DU	DU
14													DU	DU
15														DU

D = De-escalate to the next lower dose; DLT = dose-limiting toxicity; DU = current dose is unacceptably toxic;
 E = Escalate to the next higher dose; mTPI = modified toxicity probability interval; S = stay at the current dose
 Target toxicity rate = 33%
 Flat noninformative prior Beta (1,1) is used as a prior and $\varepsilon_1 = \varepsilon_2 = 0.05$

Assessment of toxicity and dose escalations or de-escalation as guided per the mTPI will be made on an ongoing basis based upon DLT-evaluable patients as defined by occurrence of DLT or completion of 21 days on study, and after review by the DMC. If dose escalation is indicated per mTPI, the DMC will recommend escalation to the next planned dose or additional dose based on review of observed toxicity. Dose escalation and de-escalation will occur independently for each schedule. Intrasubject dose escalation to the next highest dose will be permitted once that dose level is cleared by the DMC in cases where doses have been tolerated by the patient and with Medical Monitor approval (see Table 8 for a proposed dose escalation scheme).

Table 8 Sample Dose Escalation Scheme for Part 1 IV

Monotherapy Cohorts (21-day cycles)		NL-201 dose level ($\mu\text{g}/\text{kg}$)	Maximum dose that may be administered at 1 time (μg) ^a
Schedule A (D1)	Schedule B (D1+D8)		

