P-4A	P-4B	200 mg	6	600
P-5A	P-5B	200 mg	12	1200
Potential NL-201 Intermediate Dose Level^b				
P-2A-1	P-2B-1	200 mg	0.6	60
P-3A-1	P-3B-1	200 mg	1.5	150
P-3A-2	P-3B-2	200 mg	2.0	200
P-4A-1	P-4B-1	200 mg	4.0	400
P-4A-2	P-4B-2	200 mg	5.0	500
P-5A-1	P-5B-1	200 mg	7.5	750
P-5A-2	P-5B-2	200 mg	9.0	900
P-5A-3	P-5B-3	200 mg	10.0	1000

D = day; DMC = Data Monitoring Committee

- a Applicable to patients that weigh ≥ 100 kg (dose is capped as to not allow > 100 times the current dose level to be administered to a patient at 1 time)
- b At the recommendation of the DMC or based on Sponsor's determination, additional dose levels may be tested and/or cohorts may be expanded.

The MTD is defined as the highest dose for which the probability of a patient experiencing a DLT with NL-201 during Cycle 1 is $\leq 33\%$. At the discretion of the DMC, and in keeping with the pre-specified mTPI design matrix, additional dose levels may be tested to determine the RP2D (see [Table 9](#)).

Based on review of DLTs, the DMC may initiate step-dosing to improve the tolerability of NL-201, wherein 1 or more step-doses below the target dose would be provided prior to reaching the target dose (see [Section 6.2.1.4](#)). If step-dosing is used, the DLT window would extend from the first dose to 21 days after receiving the target dose (ie, would include the initial reduced-dose cycles in addition to the first target-dose cycle). Once a patient receives the intended target dose for their cohort, subsequent doses for that patient will continue at that dose level unless a delay in dosing of > 6 weeks causes washout of the drug, in which case the step-dosing regimen would be repeated if the patient is to resume dosing.

Supported by the mTPI design, the DMC will determine the RP2D for NL-201 in combination with pembrolizumab and treatment schedule (either A or B) for Part 4 by considering the PK, PDn, and any cumulative toxicities over multiple cycles of NL-201 in combination with pembrolizumab.

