6.2.1.4 Step-Dosing

Pre-clinical studies of NL-201 suggest that symptomatic toxicity of NL-201 in animals peaks with the first dose, such that symptomatic toxicity caused by subsequent doses is attenuated compared to that caused by the first dose. Dose levels that are not tolerated when given as an initial dose become tolerated after giving 1 or more initial step-doses at a reduced (tolerated) dose level, and remain tolerated in subsequent doses. Thus, if a specific dose level is not well tolerated (ie, elicits DLTs in $\geq 33\%$ of patients), it is possible that tolerability can be improved by providing 1 or more reduced doses. Once the target dose is reached, subsequent doses would be given at the expected dose level for that cohort.

If step-dosing is implemented, dosing during the first cycle of step-dosing will be administered on Day 1 and Day 8 for both Schedule A and Schedule B patients, though in subsequent cycles Schedule A patients will resume Q3W dosing while Schedule B patients will continue Day 1+8 dosing.

The Cycle 1 dose used for step-dosing will be calculated as one half of the highest tolerated initial dose (HTID), ie, the highest initial dose at which $< 33\%$ of patients experience DLTs. Subsequent cycles will increase 1 dose level (DL) at a time to the CTD.

Table 10 Step-Dosing Guidance

Steps	Cycle 1				
	D1	D8	C2	C3	C4
1	0.5 x HTID	0.5 x HTID	CTD		
2	0.5 x HTID	0.5 x HTID	HTID + 1 DL	CTD	
3	0.5 x HTID	0.5 x HTID	HTID + 1 DL	HTID + 2 DL	CTD

C = cycle; CTD = cohort target dose; D = day; DL = dose level; HTID = highest tolerated initial dose

The DLT window for each patient during step-dosing will extend to include the cycle in which the patient first receives the CTD. The DLT window for each cohort is highlighted in gray in [Table 10](#).

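### If step-dosing is used, the 21-day evaluability rule and the Cycle 1 MTD wording do not follow the protocol's extended DLT window, so a patient can count as DLT-free at a target dose not yet received or barely observed

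*Combined protocol and SAP*

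**What the plan says.** **The 21-day and Cycle 1 texts.** Table 15 counts "Patients enrolled into Part 1 or Part 3 who either complete the first 21 days of study or who experience a DLT". Section 6.2.1.1 (Part 1) bases mTPI decisions on "DLT-evaluable patients as defined by occurrence of DLT or completion of 21 days on study", and Section 6.2.1.2 (Part 3) says the same. The synopsis has the Part 1 decision "made after all DLT-evaluable patients have completed Cycle 1 and the DMC has reviewed the safety data". For the MTD, Section 6.2.1.2 reads: "The MTD is defined as the highest dose for which the probability of a patient experiencing a DLT with NL-201 during Cycle 1" is at most 33%. The synopsis and Sections 6.2.1.1 and 9.4.2 carry the same Cycle 1 limit. Section 9.2, to which 9.4.2 refers for detail, gives the definition without it. The Part 3 text of Section 6.2.1.3 places the DLT observation window in Cycle 1. None of these sentences mentions step-dosing.

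**The step-dosing texts.** The synopsis and Sections 6.2.1.1 and 6.2.1.2 state: "If step-dosing is used, the DLT window would extend from the first dose to 21 days after receiving the target dose". Section 6.2.1.4 puts it per patient: "The DLT window for each patient during step-dosing will extend to include the cycle in which the patient first receives the CTD". Table 10 gives half the highest tolerated initial dose on Days 1 and 8 of Cycle 1. The cohort target dose (CTD) first appears in Cycle 2, 3 or 4 for one, two or three steps. The Part 1 text of Section 6.2.1.3 also reaches past the CTD.

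**Replacement.** Section 4.1.3 replaces patients who cannot be evaluated during the DLT window because of progression or unrelated adverse events.

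**The concern.** DLT is a primary endpoint in all parts, and Section 9.2 says the Part 2 dose will not exceed the MTD. The mTPI matrices take two inputs: the number of DLTs and the number of patients at the dose level. Without step-dosing, 21 days, Cycle 1 and the DLT window coincide and there is no problem.

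With step-dosing they separate. A patient can satisfy Table 15 at Day 21 and be tallied as DLT-free at a cohort dose that has not been given. A DLT that follows is then absent from the first input when the decision is made. A patient who leaves between Day 21 and the target dose stays in the second input. Both errors lean toward escalation.

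**Working it through.** **1. Reproduce the plan's matrices.** Inputs are Beta(1,1) with target 33% and epsilon 0.05 (Figure 5), and Beta(1,1) with target 30% and epsilon 0.03 (Figure 6). For x DLTs in n patients the posterior is Beta(1+x, 1+n−x). The action is the interval with the largest probability per unit length. Figure 5 intervals are 0–0.28 (E), 0.28–0.38 (S) and 0.38–1 (D).

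- 0/3: P(p>c) = (1−c)^4, giving 0.269 at 0.28 and 0.148 at 0.38. E: 0.731/0.28 = 2.61. S: 0.121/0.10 = 1.21. D: 0.148/0.62 = 0.24. Result: E.
- 1/3: P(p>c) = (1−c)^4 + 4c(1−c)^3, giving 0.687 and 0.510. E: 0.313/0.28 = 1.12. S: 0.177/0.10 = 1.77. D: 0.510/0.62 = 0.82. Result: S.

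The DU cut-off is not stated. Assuming DU when P(p > target) > 0.95, all 105 cells for 0–8 DLTs and n = 2–15 match in each figure. A cut-off of 0.90 gives 7 mismatches in Figure 5 and 9 in Figure 6. The matrices are sound; the issue is what is fed into them.

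**2. Calendar under step-dosing.** With 21-day cycles and k steps, the nominal target-dose day is 1 + 21k and the window closes 21 days later.

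| Steps | Target dose, nominal day | Window closes, about day | Evaluable under Table 15 |
|---|---|---|---|
| 1 | 22 | 43 | Day 21 |
| 2 | 43 | 64 | Day 21 |
| 3 | 64 | 85 | Day 21 |

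Visit windows soften the first row. Table 3 (Schedule A with step-dosing) allows Cycle 2 Day 1 ±3 days, so a one-step patient could receive the target dose about Day 22 − 3 = Day 19. Day 21 then gives only 2–3 days of observation at that dose.

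**3. Effect on the printed actions.** The cells below are the same in Figures 5 and 6.

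| What happens | Tally under the 21-day rule | Tally over the full window |
|---|---|---|
| One DLT after Day 21 | 0/3 = E | 1/3 = S |
| One DLT after Day 21 | 1/3 = S | 2/3 = D |
| One DLT after Day 21 | 3/6 = S | 4/6 = DU |
| One leaver before the target dose | 2/4 = S | 2/3 = D |
| One leaver before the target dose | 1/6 = E | 1/5 = S |

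**4. Cross-check of the counting rules.** A patient who completes Day 21 and then progresses before the target dose is DLT-evaluable under Table 15 and also due for replacement under Section 4.1.3. One who leaves for another reason, such as withdrawn consent, meets Table 15 and is not covered by the replacement rule. In Part 3, a DLT in the target-dose cycle falls inside the window of Section 6.2.1.2 and outside that of Section 6.2.1.3.

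**The case against.** The strongest reply is that this is a default with a stated exception. The 21-day rule describes the base design. The extended window follows in the same sections, and Section 6.2.1.4 states it for each patient and says Table 10 shades it for each cohort. The Part 1 DLT definition covers the CTD, and replacement is tied to the DLT window. A DMC that escalated at Day 21 would have to disregard all of this. Step-dosing is also optional, the mTPI only guides, and Table 15 still counts a later DLT once it occurs. A full statistical analysis plan and a Cohort Management Plan are announced and could align the text.

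Much of this stands. The intent is clear, and the defect is an exception that was not carried through. A reader might infer that the protocol offers two rival windows with nothing to choose between them, or that the DMC would in practice escalate on an unobserved dose. The documents do not support either for Part 1. Only for Part 3 do two sections actually disagree on the window.

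What does not stand is that the gap is harmless. The window sentences say how long DLTs are looked for. They do not say when a DLT-free patient may be counted, and the sentences that do say so give 21 days. No passage requires the DMC to wait, and a later document should not have to overrule protocol text that governs live dose decisions.

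**Conclusion.** The point holds, conditional on step-dosing, and should be fixed. The evaluable-population rule, the Part 1 decision timing and four of the five MTD statements (all but Section 9.2) do not match the protocol's own window. A single misclassified patient is enough to change the printed action at n = 3 to 6. This rests on a literal reading of Table 15, nominal 21-day cycles without dose delays, and the printed matrices.

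Three stronger readings should be resisted.

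- A reader might want to quote an inflated probability of escalation. The documents do not give the share of DLTs that would fall after Day 21, and Section 6.2.1.4 expects symptomatic toxicity to lessen after the first dose, so the share could be small.
- A reader might say that no patient can have had the target dose by Day 21. With one step on Schedule A, the visit window allows it.
- A reader might add that the delay-based DLT criteria cannot be met inside the window. That is a separate matter, and the claim is too strong: the Part 3 criterion names the start of Cycle 2 and so looks past Cycle 1.

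**What to change.** - In Table 15 and Sections 6.2.1.1 and 6.2.1.2, define DLT-evaluable as having a DLT in, or completing, the applicable DLT window that the protocol already states.
- Tie the synopsis decision timing to that window. Use the same words in every MTD definition (synopsis, 6.2.1.1, 6.2.1.2, 9.2 and 9.4.2).
- State that patients replaced under Section 4.1.3 are not in the DLT-evaluable set.
- Ask the sponsor to reconcile the Part 3 window sentence in Section 6.2.1.3 with Sections 6.2.1.2 and 6.2.1.4.

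**Cost.** The change is wording only and has no effect unless step-dosing starts. If it does, decisions wait for the protocol's own window to close, and more patients may need replacement against the Part 3 limit of 21 per schedule (Section 4.1.2).

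As an illustration, assume exponential time on treatment with the 3-month median in Section 4.1.1 (taken as 91 days). Of 21 patients who complete Day 21, the number completing the window is 21 × 2^(−t/91), where t is the time from Day 21 to window close:

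- one step, t = 22: 21 × 0.846 = 17.8
- two steps, t = 43: 21 × 0.721 = 15.1
- three steps, t = 64: 21 × 0.614 = 12.9

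That is about 18, 15 and 13. For three steps, medians of 60 to 120 days give 10.0 to 14.5. These counts leave out patients who become evaluable through a DLT.

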9.4 Statistical Analyses

9.4.1 General Considerations

Demographic data and disease-related characteristics will be summarized separately for Part 1, by schedule (eg, IV Schedule A, IV Schedule B), and Part 2, by expansion cohort. Descriptive statistics (count and percent, mean, median, standard deviation, minimum, maximum) will be used. All patient data, efficacy and safety data will be summarized. Data from Parts 3 and 4 (NL-201 in combination with pembrolizumab) will be summarized in a similar manner.

A full Statistical Analysis Plan will be prepared to describe in full the statistical methods and analyses to be applied to the data arising in this study.

9.4.2 Determination of MTD in Part 1 and Part 3

For each schedule (IV Schedule A, IV Schedule B) in Part 1 (NL-201 monotherapy), the determination of MTD will be the highest dose for which the probability of a patient experiencing a DLT with NL-201 during Cycle 1 is $\leq 33\%$. Refer to [Section 9.2](#) for more details.

Similarly, for each schedule separately in Part 3 (NL-201 in combination with pembrolizumab), the determination of MTD will be the highest dose for which the probability of a patient experiencing a DLT with NL-201 during Cycle 1 is $\leq 33\%$. Refer to [Section 9.2](#) for more details.

9.4.3 Assessment of Preliminary Efficacy in Part 2 and Part 4

For NL-201 monotherapy, while tumor response data based on both RECIST 1.1 and iRECIST will be collected from all patients in dose escalation and expansion, formal analysis of tumor response will only be performed for the expansion cohorts in Part 2 based on iRECIST. Results will be presented and summarized using an exact 95% binomial confidence interval.

Other response-related efficacy parameters including time to response, duration of response, and clinical benefit rate will be also summarized by Part 2 expansion cohort.

In expansion cohorts in Part 2, OS and progression free survival (defined as the time from study entry to the time of disease progression or death from any cause) will be displayed graphically using Kaplan-Meier plots. Median PFS and OS will be extracted from the Kaplan-Meier plots along with their associated 95% confidence intervals. PFS and OS rates at 3 monthly intervals will also be extracted. Patients who do not experience progression or death will be censored at their last clinic visit contact for the assessment of disease progression.

For NL-201 in combination with pembrolizumab, data from Part 4 dose expansion cohort will be summarized and analyzed in a similar manner.

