3 OBJECTIVES AND ENDPOINTS

Parts 1 and 2 (NL-201 Monotherapy)

OBJECTIVES	ENDPOINTS
Primary	

 Assess the safety and toxicity profile of NL-201 in patients with advanced solid tumors Define the recommended phase 2 dose (RP2D) and schedule of NL-201 	
 Dose-limiting toxicities (DLTs) Incidence and severity of treatment-emergent adverse events and clinically significant changes in vital signs, electrocardiograms (ECGs), and clinical laboratory tests
Secondary	

 Characterize the pharmacokinetic (PK) profile of NL-201 	
 PK parameters including but not limited to area under the serum concentration time curve (AUC), maximum observed serum concentration (C_{max}), half-life ($t_{1/2}$), clearance (CL), and volume of distribution (Vd)

 Estimate the immunogenicity of NL-201 	
 Antidrug antibodies in serum during and after treatment with NL-201

 Estimate the antitumor activity of NL-201 per Response Evaluation Criteria in Solid Tumors (RECIST) 1.1 and RECIST for use in cancer immunotherapy trials (iRECIST) criteria 	
 Best objective response Objective response rate Duration of response Progression-free survival (PFS)
Exploratory	

 Investigate the pharmacodynamic biomarkers of NL-201 	
 Flow-cytometry analysis of immune cells in blood, eg, for markers of T-cell activation and exhaustion, eg, cluster of differentiation (CD)4, CD8, CD25, forkhead box P3 (FoxP3) Serum measurements of inflammatory cytokine levels Analysis of immune characteristics of the tumor microenvironment (eg, multiplex immunohistochemical, transcriptional profiling)

 Estimate additional measures of antitumor activity of NL-201 per RECIST 1.1 and/or iRECIST criteria 	
 Overall survival (OS) Clinical benefit rate

Parts 3 and 4 (NL-201 in Combination with Pembrolizumab)

OBJECTIVES	ENDPOINTS
Primary	

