
 Assess the safety and tolerability of NL-201 in combination with pembrolizumab in patients with advanced solid tumors Define the RP2D and schedule of NL-201 in combination with pembrolizumab 	
 DLTs Incidence and severity of treatment-emergent adverse events and clinically significant changes in vital signs, ECGs, and clinical laboratory tests
Secondary	

 Characterize the PK profile of NL-201 in combination with pembrolizumab 	
 NL-201 PK parameters including but not limited to AUC, C_{max}, $t_{1/2}$, CL, and Vd

OBJECTIVES	ENDPOINTS

 Estimate the immunogenicity of NL-201 in combination with pembrolizumab 	
 NL-201 antidrug antibodies in serum during and after treatment with NL-201 in combination with pembrolizumab

 Estimate the antitumor activity of NL-201 in combination with pembrolizumab per RECIST 1.1 and iRECIST criteria 	
 Best objective response Objective response rate Duration of response PFS
Exploratory	

 Investigate the pharmacodynamic biomarkers of NL-201 in combination with pembrolizumab 	
 Flow-cytometry analysis of immune cells in blood for modulation of lymphocyte subsets, including markers of T-cell activation and exhaustion, including CD4, CD8, CD25, FoxP3 Serum measurements of inflammatory cytokine levels Analysis of immune characteristics of the tumor microenvironment (eg, multiplex immunohistochemical, transcriptional profiling)

 Evaluation of exploratory biomarkers including pharmacodynamic and potential patient selection biomarkers 	
 PD-L1 expression in tumors (as available) Tumor microenvironment (TME) immune score (as available)

 Estimate additional measures of antitumor activity of NL-201 in combination with pembrolizumab per RECIST 1.1 and/or iRECIST criteria 	
 OS Clinical benefit rate

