For Parts 2 and 4 radiologic follow-up should continue until radiologic disease progression, start of a new anti-cancer treatment, loss to follow-up, or death.

CR and PR require confirmation by a repeat assessment no earlier than 4 weeks after the imaging criteria for response is first met.

Tumor images to determine tumor assessment/response rates and PFS will be evaluated based on RECIST 1.1 and additionally on iRECIST. For more detailed guidance on RECIST 1.1 please refer to the original publication³⁰ and 2 further publications should be considered in case of need for further definitions.^{32,33}

For details regarding methods of lesion measurement and tumor response, see [Section 10.6](#).

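### Section 9.4.3 confines the formal tumor response analysis to iRECIST, so no RECIST 1.1 response rate with a confidence interval is prespecified although the secondary objective names both criteria

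*Combined protocol and SAP*

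**What the plan says.** Section 3 gives the secondary efficacy objective for Parts 1 and 2 as "Estimate the antitumor activity of NL-201 per Response Evaluation Criteria in Solid Tumors (RECIST) 1.1 and RECIST for use in cancer immunotherapy trials (iRECIST) criteria", and for Parts 3 and 4 as "Estimate the antitumor activity of NL-201 in combination with pembrolizumab per RECIST 1.1 and iRECIST criteria". The endpoints under each are best response, ORR, duration of response and PFS.

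Section 8.2.1, on imaging, states: "Tumor images to determine tumor assessment/response rates and PFS will be evaluated based on RECIST 1.1 and additionally on iRECIST".

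Section 9.4.3 says of monotherapy that "tumor response data based on both RECIST 1.1 and iRECIST will be collected from all patients in dose escalation and expansion", but that "formal analysis of tumor response will only be performed for the expansion cohorts in Part 2 based on iRECIST". The exact 95% binomial interval follows directly on that sentence. Time to response, duration of response, clinical benefit rate and PFS are then listed for the Part 2 cohorts with no criterion attached. For the combination, "data from Part 4 dose expansion cohort will be summarized and analyzed in a similar manner".

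Section 9.4.1 adds two general statements: "All patient data, efficacy and safety data will be summarized", and "A full Statistical Analysis Plan will be prepared to describe in full the statistical methods and analyses to be applied". Section 9.2 sets out the Part 2 Simon design (18 patients, stop at no responses, otherwise 12 more) in terms of objective responses, without saying by which criterion.

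**The concern.** The objective asks for two estimates of activity and the analysis section formally provides for one. The missing one is RECIST 1.1, which Section 8.2.1 puts first, with iRECIST as the addition.

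The criteria are not interchangeable here. Section 10.6.3 says that an unconfirmed progression under iRECIST does not prevent a later response from being assigned, and that iRECIST, unlike RECIST 1.1, needs progression to be confirmed. Section 6.1.1.1 allows treatment past RECIST 1.1 progression for this reason. An iRECIST response rate can therefore include responses that RECIST 1.1 would not count, and progression dates can differ too.

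If only the iRECIST rate is formally reported, readers cannot tell how far the result depends on that feature. In an open-label, single-arm expansion with few expected responses, the criterion should be settled before the data are seen.

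**Working it through.** **Step 1. Which criterion is fixed for which analysis.**

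| Item | Criterion in the documents | Where |
|---|---|---|
| Secondary objective, all parts | RECIST 1.1 and iRECIST | Section 3 |
| Image evaluation for response rates and PFS | RECIST 1.1, additionally iRECIST | Section 8.2.1 |
| Data collected (monotherapy) | Both | Section 9.4.3 |
| Formal response analysis, Part 2 | iRECIST alone | Section 9.4.3 |
| Part 4 analysis | By analogy with Part 2 | Section 9.4.3 |
| Duration of response, PFS | None named | Section 9.4.3 |
| Stage 1 and final two-stage decisions | None named | Section 9.2 |
| Radiologic follow-up after stopping treatment, Parts 2 and 4 | RECIST 1.1 | Section 4.1 |

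The fourth row is narrower than the three above it. The sixth and seventh are open. One could read the fourth row as also governing the two-stage test, but Section 9.2 does not say so.

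**Step 2. When the criteria can give different answers.** A footnote to Table 20 says that the response categories coincide if no pseudoprogression occurs. The difference is therefore confined to patients with an apparent progression before a response. The documents do not say how many to expect.

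**Step 3. Check of the interval method.** The Clopper-Pearson limits for x responders in n patients are

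- lower = 2.5th percentile of Beta(x, n − x + 1)
- upper = 97.5th percentile of Beta(x + 1, n − x)

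With n = 30 these reproduce Table 14:

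- 6/30: 0.0771 and 0.3857, that is (7.7%, 38.6%)
- 9/30: 0.1473 and 0.4940, that is (14.7%, 49.4%)
- 12/30: 0.2266 and 0.5940, that is (22.7%, 59.4%)

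**Step 4. What one discordant patient does (counts assumed for illustration).** Suppose three patients in a cohort of 30 respond under iRECIST, one of them only after a RECIST 1.1 progression.

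- RECIST 1.1: 2/30 = 6.7%, 95% CI 0.8% to 22.1%
- iRECIST: 3/30 = 10.0%, 95% CI 2.1% to 26.5%
- Difference: 1/30 = 3.3 percentage points

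**Step 5. Why the decision criterion needs a name.** Stage 1 stops at 0/18. If the only response among the first 18 patients is seen under iRECIST alone, the count is 0/18 by RECIST 1.1 (stop) and 1/18 by iRECIST (continue). The same data support opposite decisions, and Section 9.2 does not choose between them.

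**The case against.** The strongest reply is that the protocol restricts only the formal analysis. Section 9.4.1 promises a summary of all efficacy data and a full Statistical Analysis Plan that is not among the documents. The objective is one of estimation, secondary to safety in a Phase 1 study, and iRECIST is a natural choice for an immune agonist, as Sections 6.1.1.1 and 10.6.3 explain.

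Much of this stands. A reader might infer that the RECIST 1.1 data will never be analysed. The documents do not support that: the general commitment covers them, and the later plan may include them. What the reply does not remove is the specific restriction. A general promise to summarize does not supply a RECIST 1.1 ORR with an interval, and a later plan that follows Section 9.4.3 would carry the gap forward.

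Two other stronger readings also fail.

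- **That Section 3 ranks RECIST 1.1 first and Section 9.4.3 reverses it.** Section 3 lists the criteria side by side. Only the imaging section treats iRECIST as additional.
- **That using iRECIST inflates the type I error of the Part 2 test.** This would need the 2.5% null to be a RECIST 1.1 rate, a final rejection boundary, and a rate of iRECIST-only responses. The documents give none of these. If the null is an iRECIST rate, there is no inflation. Adding RECIST 1.1 tables would not change the test's error rate in any case.

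**Conclusion.** The point holds in a limited form. Section 9.4.3 prespecifies a formal response analysis under one of the two criteria that the secondary objective names, and extends that approach to Part 4. The criterion for duration of response, PFS and the two-stage decisions is left open; it is not set to iRECIST.

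The size is modest. Each response credited only under iRECIST is worth 3.3 percentage points of ORR in a cohort of 30, and in Stage 1 a single such response could decide whether a cohort continues. Both statements rest on assumed counts. With no pseudoprogression the two response rates would agree, and the separate RECIST 1.1 table would simply show that. The primary safety objectives and the sample sizes are unaffected. The change is worth making because it is cheap and aligns the analysis with the stated objective.

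**What to change.** In Section 9.4.3, remove the restriction to iRECIST. State that, for each Part 2 and Part 4 cohort, ORR with an exact 95% interval, best response, duration of response and PFS will be reported under both RECIST 1.1 and iRECIST. Add a listing of patients whose response or progression status differs between the two. Carry the same wording into the full Statistical Analysis Plan.

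In Section 9.2, name the criterion that drives the Stage 1 and final decisions of the two-stage design. It may remain iRECIST, provided this is stated and the 2.5% and 15% rates are understood on the same criterion.

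The cost is the amended wording and one extra set of tables and listings from data already collected. No visits, scans or patients are added.
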